### **8.1.1 Rationale for discontinuation of trial treatment criteria**

No 1-4 are included to protect the patient's safety.

No 5 and 8 are included not to confound the effects of the investigational product.

No 6 and 7 (and no. 9 for France only) are included to protect the patient's safety.

### **8.2 Withdrawal from the trial**

A patient may withdraw consent at any time at his own request, or at the request of the patient's parent or the patient's legally acceptable representative (LAR).

If a patient withdraws consent, the investigator must ask the patient if he is willing, as soon as possible, to have assessment performed according to EoT visit. See the flowchart for data to be collected.

Final drug accountability must be performed even if the patient is not able to come to the trial site. A treatment discontinuation session must be made in the IWRS.

If a patient withdraws from the trial, he may request destruction of any samples taken and not tested, and the investigator must document this in the medical record.

If the patient withdraws consent, Novo Nordisk may retain and continue to use any data collected before such a withdrawal of consent.

Although a patient is not obliged to give his reason(s) for withdrawing, the investigator must make a reasonable effort to ascertain the reason(s), while fully respecting the patient's rights. Where the reasons are obtained, the primary reason for withdrawal must be specified in the EoT form in the eCRF.

If relevant a follow-up phone call may be requested.

#### **8.2.1 Replacement of patients**

Patients who discontinue trial product or withdraw from trial will not be replaced.

### **8.3 Lost to follow-up**

A patient will be considered lost to follow-up if he repeatedly fails to return for scheduled visits and is unable to be contacted by the trial site.

The following actions must be taken if a patient fails to return to the trial site for a required visit:

- The site must attempt to contact the patient and reschedule the missed visit as soon as possible and counsel the patient on the importance of maintaining the assigned visit

Protocol  
NN7088-4410

~~CONFIDENTIAL~~

Date:  
Version:  
Status:  
Page:

18 June 2019  
2.0  
Final  
33 of 86

**Novo Nordisk**

schedule and ascertain whether or not the patient wishes to and/or should continue in the trial.

- Before a patient is deemed lost to follow-up, the investigator must make every effort to regain contact with the patient (where possible, at least three telephone calls and, if necessary, a certified letter to the patient's last known mailing address or local equivalent methods). These contact attempts should be documented in the patient's source document.
- Should the patient continue to be unreachable, he will be considered to have withdrawn from the trial with a primary reason of lost to 'follow-up'.

## 9 Trial assessments and procedures

Trial procedures and their timing are summarised in the flowchart, see section 2.

All screening evaluations must be completed and reviewed to confirm that potential patients meet all eligibility criteria.

[figure not shown]
The investigator will maintain a screening log to record details of all patients screened and to confirm eligibility or record reason for screen failure, as applicable.

At screening, patients will be provided with a card stating that they are participating in a trial and giving contact details of relevant trial site staff.

Adherence to the trial design requirements, including those specified in the flowchart, is essential and required for trial conduct.

Any scheduled assessment visit (V1, V3, V5, V7, and EoT) must be rescheduled if the patient has experienced a treatment required bleeding episodes within the last 7 days prior to the visit date.

**Figure 9-1 Visit structure**

Next visit in line must be calculated based on screening/V1.

Review of completed diaries, PRO questionnaires for possible AEs, and laboratory reports must be documented either on the trial documents or in the patient's source documents. If clarification of entries or discrepancies in the diary or possible AEs in PRO questionnaires is needed, the patient must be questioned and a conclusion made in the patient's source documents. Care must be taken not to bias the patient.

Informed consent must be obtained before any trial related activity, see [Appendix 3](#).

### 9.1 Follow-up visit (only for patients who have developed a FVIII inhibitors)

#### For patients who discontinues trial product due to an inhibitor development:

1 month after the EoT visit the patient should attend a FU Visit. Assessments should be according to flowchart, see section 2. Additional follow-up visits may be arranged at intervals as long as

Protocol  
NN7088-4410~~CONFIDENTIAL~~Date:  
Version:  
Status:  
Page:18 June 2019  
2.0  
Final  
35 of 86

Novo Nordisk

clinically warranted. If the patient refuses to attend the follow-up visit, the persuading attempts should be documented in the patient's source document.

### **For patients who continues on trial product with a low titre inhibitor:**

Patients with low titre inhibitor ( $\geq 0.6$  and  $\leq 5$  BU) continuing in the trial must follow the prescribed regimen and the scheduled visits as described in the flowchart. If closer monitoring is needed patients with low titre inhibitors should attend a follow-up visit with blood collection for the assessments specified in the flowchart [Appendix 20](#) (Follow-up (inhibitors)). Closer monitoring is highly recommended but this decision will be Investigator's discretion.

### **9.2 Follow-up visit (only for patients discontinued trial product due to lack of efficacy or anaphylaxis)**

In case of discontinuation of trial product due to lack of efficacy (discontinuation criteria no. 2) or anaphylaxis to the trial product (discontinuation criteria no. 4), the patient should be scheduled for an EoT visit as soon as possible and asked to attend a follow-up visit 1 months after EoT.

Assessment should be done according to the flowchart in section [2](#)

If the patient refuses to attend the follow-up visit, the patient should be considered as lost to follow-up, see section [8.3](#).

The follow-up visit can be performed as either a telephone call or a site visit at the investigator's and/or patient's discretion.

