## 8 Discontinuation/Withdrawal criteria

The patient may be discontinued at any time during the trial at the discretion of the investigator for safety, behavioural, compliance or administrative reasons.

Efforts must be made to have the patients, who discontinue trial product, attend EoT visit to collect the required data for the analysis of the primary (and confirmatory secondary) endpoint. Only patients who withdraw consent will be considered as withdrawn from the trial. Patients must be educated about the continued scientific importance of their data, even if they discontinue trial product.

For patients shifting to commercial products see section [5.2.1](#).

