### 8.1 Discontinuation of trial treatment

The patient must be discontinued from trial product, if the following applies:

1. Included in the trial in violation of the inclusion and/or exclusion criteria
2. Lack of haemostatic effect of the trial product. The bleed is not controlled after 48 hours of appropriate turoctocog alfa pegol treatment
3. FVIII inhibitor (>5 BU) as confirmed by re-testing by Central Laboratory
4. Allergy/anaphylaxis to the trial product requiring systemic treatment
5. Treatment with other FVIII containing products other than trial product turoctocog alfa pegol or anti-coagulants (therapeutic doses)
6. Incapacity or unwillingness to follow the trial procedures
7. FVIII inhibitor ( $\geq 0.6$  and  $\leq 5$  BU) as confirmed by re-testing by Central Laboratory that makes treatment (prophylaxis and/or treatment of bleeding episodes) with turoctocog alfa pegol clinically ineffective
8. Simultaneous participation in another clinical trial of an approved or non-approved investigational medicinal product.
9. Applicable for France only; In the case of a major thromboembolic event (e.g. myocardial infarction, cerebrovascular disease or deep venous thrombosis) as per investigator.

See the flowchart for data to be collected at the time of treatment discontinuation and follow-up and for any further evaluations that need to be completed.

The primary reason for discontinuation of trial product must be specified in the EoT form in the eCRF, and final drug accountability must be performed. A treatment discontinuation session must be made in the IWRS.

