**9.6.3 Follow-up on AEs and SAEs**

After the initial AE/SAE report, the investigator is required to proactively follow each patient at subsequent visits/contacts. All SAEs, and non-serious AESIs (as defined in Section [9.6.1.1](#)), will be followed until resolution, stabilization, or if the event is otherwise explained (e.g. chronic condition) or the patient is lost to follow-up (as defined in Section [8.3](#)). Further information on follow-up procedures is given in [Appendix 4](#).

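### Protocol 9.2 labels a reachable patient who declines the 1-month follow-up visit as lost to follow-up, against the definition in 8.3, and leaves it unclear whether his open SAEs are still followed

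*Protocol*

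**What the plan says.** Six places in the protocol bear on the point.

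- **9.2** concerns patients stopped under discontinuation criterion 2 or 4. They should have an EoT visit promptly and are asked to a follow-up visit one month later, by telephone or at the site. On refusal: "If the patient refuses to attend the follow-up visit, the patient should be considered as lost to follow-up", with a reference to 8.3.
- **8.3** applies the term to a patient "if he repeatedly fails to return for scheduled visits and is unable to be contacted by the trial site". Before using it the site must try hard to regain contact, by repeated calls and a letter if needed. If he stays unreachable, "he will be considered to have withdrawn from the trial with a primary reason of lost to" follow-up.
- **8** states: "Only patients who withdraw consent will be considered as withdrawn from the trial".
- **9.1** deals with the same refusal by a patient stopped for an inhibitor. There, "the persuading attempts should be documented" in the source record, and no label follows.
- **9.6.3** has SAEs and non-serious AESIs followed until they resolve, stabilise or are otherwise explained, "or the patient is lost to follow-up" in the sense of 8.3. **Appendix 4** keeps the AE outcome Unknown for patients lost to follow-up.
- **8.1** requires: "The primary reason for discontinuation of trial product must be specified in the EoT form in the eCRF". Section 8.2 names the reason for withdrawing from the trial as a separate item on that form.

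The SAP has no rule on disposition reasons or on loss to follow-up.

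**The concern.** Section 9.2 sends the site to a definition that its own case does not meet. A refusal is a contact with an answer, whereas loss to follow-up is the absence of contact. Treating one as the other makes the follow-up status wrong for a patient whose whereabouts and wishes are known.

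The group makes this more than a matter of wording. Safety is the primary objective, and section 3.3 names inhibitor development and allergic/hypersensitivity reactions as the key risks. Patients stopped under criterion 4 have had such a reaction, and those stopped under criterion 2 are treatment failures. If the label is taken at face value, a site could stop pursuing a serious reaction still open at EoT and code its outcome Unknown, although a further enquiry might have settled it. Another site, reading 8.3 strictly, would carry on. The same case would then be handled in two ways.

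**Working it through.** No arithmetic decides this, and the plan gives no figure that depends on it. The check is to take one patient through the sections: stopped under criterion 2 or 4, reached by the site, declines the one-month visit, consent not withdrawn.

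| Question | Section | Answer for this patient |
|---|---|---|
| What status does he get? | 9.2 | Should be considered lost to follow-up |
| Has he repeatedly failed to return? | 8.3, first condition | Not necessarily; one refusal is enough for 9.2 |
| Is he impossible to contact? | 8.3, second condition | No; he has answered |
| Is he withdrawn from the trial? | 8.3 | Only if the label carries its consequence over; the clause is written for unreachable patients |
| Is he withdrawn from the trial? | 8 | No; consent has not been withdrawn |
| How would an inhibitor patient be treated? | 9.1 | Attempts documented, no label |
| Is the reason for stopping product affected? | 8.1, 8.2 | No; it belongs on the EoT form, and nothing says a later status replaces it |
| Does follow-up of an open SAE end? | 9.6.3 | Depends on the reading, see below |

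**Status.** The conditions in 8.3 are joined by *and*. The second fails for anyone who refuses, so 9.2 contradicts the section it cites. It also sits badly with section 8 and differs from 9.1 with no reason given.

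**Open SAEs.** There are two readings.

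1. Section 9.2 declares him lost to follow-up with reference to 8.3, and 9.6.3 stops at loss to follow-up with reference to 8.3. So follow-up may stop, and Appendix 4 makes the outcome Unknown available.
2. Section 9.6.3 stops only for patients who meet the 8.3 definition. He does not, so follow-up continues.

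The text supports both. The AESI part of 9.6.3 adds little, because inhibitors are the only AESI (Table 9-7) and refusals by those patients fall mainly under 9.1.

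**Size.** Section 5.2 expects 170 patients assigned and 153 completing: 170 − 153 = 17, or 17/170 = 10%, for all reasons together. How many would stop under criterion 2 or 4, and how many of those would refuse the visit, is not stated, so no count or percentage of affected patients can be derived.

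**Primary endpoint.** Under 9.6.1 AEs are collected to EoT, or to the follow-up visit where one applies. If the patient attended EoT, only the month after it is at stake.

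**The case against.** The strongest reply is that this is a loose cross-reference with little practical effect.

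- The verb in 9.2 is *should*, and the visit may be a telephone call. The sentence therefore reaches only a patient who declines even a call.
- Section 8.3 requires real efforts at contact before the label is used.
- Other duties remain. Appendix 4 obliges the investigator to arrange further evaluations where indicated, with severe hypersensitivity as an example. Section 9.8.8.3 asks that anaphylaxis patients be followed for inhibitors. Section 9.6.1 requires notification of related SAEs learned of after the trial.
- Appendix 4 permits the outcome Unknown but does not require it. The category for events not recovered also takes in cases where the outcome is not known.

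All of this stands, and it limits the size of the problem. It does not remove the contradiction. The effort required by 8.3 is aimed at patients who cannot be found and gives no guidance on one who has answered. The remaining duties do not say whether routine SAE follow-up continues for him.

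Two stronger readings are tempting and not supported. A reader might infer that the label replaces lack of effect or anaphylaxis as the recorded reason for stopping N8-GP. Section 8.1 puts that reason on the EoT form, 8.2 names the withdrawal reason separately, and neither document says one overwrites the other. A reader might also infer that the duty to follow the patient's SAEs definitely ends. Section 9.6.3 ties the end to the 8.3 definition, which he fails, so the text allows that reading without requiring it.

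**Conclusion.** The point holds as a misclassification rule. Section 9.2 gives a reachable patient a status that conflicts with 8.3, does not fit section 8 and differs from 9.1. The effect is on his trial-withdrawal or follow-up status. On one of two available readings, the rule also lets follow-up of an open SAE stop and its outcome be coded Unknown while he could still be asked.

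The number of patients is unknown and probably small, and the effect on the AE count is confined to about one month after EoT. That limit assumes the patient attended EoT, which 9.2 asks for but cannot guarantee. The change is still worth making: it concerns patients who stopped for a safety or efficacy reason, and the inconsistency costs almost nothing to remove.

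**What to change.** Reconcile 9.2 with 8, 8.3, 9.1 and 9.6.3:

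1. In 9.2, replace the sentence on refusal with the rule already used in 9.1: document the attempts in the source record. Enter *follow-up visit refused* as a status of its own.
2. Reserve lost to follow-up for patients who meet both conditions in 8.3, and align 8.3 with section 8 on who counts as withdrawn.
3. In 9.6.3, state that declining this visit does not by itself end follow-up of open SAEs while information can still be obtained with the patient's consent.

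Section 8.1 needs no change. The cost is a few sentences and one status category, with no added visits or samples and no change to the planned analyses.

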### **9.3 Unscheduled visit**

The Unscheduled visit form in eCRF must be filled in if the patient attends an unscheduled visit due to the following reasons:

#### **Suspicion/confirmation of inhibitor development**

- Vital signs according to section [9.6.4](#)
- Coagulation parameters according to [Appendix 2](#)
- FVIII activity according to [Appendix 2](#)
- Antibodies according to [Appendix 2](#)

#### **Re-sampling of inhibitor blood samples**

- Antibodies according to [Appendix 2](#)

#### **Severe allergic reaction/anaphylaxis**

- Vital signs according to section [9.6.4](#)

Protocol  
 NN7088-4410

~~CONFIDENTIAL~~

Date:  
 Version:  
 Status:  
 Page:

18 June 2019  
 2.0  
 Final  
 36 of 86

**Novo Nordisk**

- Antibodies (in case of severe allergic reactions) according to [Appendix 2](#)

For any other reason, the visit should be documented according to local practice.

#### 9.4 Patient related info/assessments

**Demography** consists of date of birth and age (unless not allowed according to local regulation, see [Appendix 8](#)), ethnicity and race (unless not allowed according to local regulation, see [Appendix 8](#))

A **concomitant illness** is any illness other than haemophilia that is present at the start of the trial (i.e. at the first visit) or found as a result of a screening procedure or other trial procedures performed before exposure to trial product.

**Medical history** is a medical event other than haemophilia that the patient has experienced in the past. This will include joint status at screening:

- List of joints which during the patient’s life have caused special problems, in terms of repeated or frequent bleeding episodes. This list can be compiled through discussion between the patient/parent(s) and investigator
- List of joints with arthropathy

In case of an abnormal and clinically significant finding other than haemophilia, the investigator must record the finding on the Medical History/Concomitant Illness form if it is present at screening. Any new finding fulfilling the AE definition (see [Appendix 4](#)) during the trial and any clinically significant worsening from baseline (Screening/V1) must be reported as an AE (see Section [9.6](#)).

**Details of haemophilia / haemophilia treatment and bleed history** is any data from the previous trial NN7088-3859 (pathfinder2) or NN7088-3885 (pathfinder5) in relation to previous regimens and bleeding episodes.

**Genotype testing** during trials NN7088-3859 (pathfinder2) and NN7088-3885 (pathfinder5) was offered to all patients unless not allowed according to local regulation.

**AB0 blood group** will be collected in eCRF as A, B, AB, 0 or not assessed based on medical records

**Concomitant medication** is any medication, other than the trial product, that is taken during the trial

Available demography, details of haemophilia treatment and bleeding episodes, and genotype will be transferred from previous trial NN7088-3859 (pathfinder2) or NN7088-3885 (pathfinder5).

#### **9.4.1 Physical examinations**

A physical examination will include assessments of the general appearance, head, ears, eyes, nose, throat and neck, respiratory system, cardiovascular system, gastrointestinal system, including mouth, musculoskeletal system, central and peripheral nervous system (general evaluation and neurological assessment), skin, and lymph node palpation.

Following aspects of the neurological examination will be assessed:

- General appearance including language, social and developmental aspects
- Parameters including handedness, head circumference and level of consciousness
- Cranial
- Extremity and truncal tone
- Strength of extremities
- Reflexes
- Sensory aspects
- Gait with regards to walking, running, and standing
- Coordination and fine motor skills

Remember to update medical history if clinical findings have been recorded previously.

#### **9.5 Efficacy assessments**

Planned time points for all efficacy assessments are provided in the flowchart.

##### **9.5.1 Bleeding episodes**

The following must be recorded for any bleeding episode, also bleeding episodes that do not require treatment with trial product:

- Start date and time
- Stop date and time (see [Table 9-1](#) for definition)
- Anatomical location(s)
- Cause (see [Table 9-2](#) for definitions)
  - spontaneous
  - traumatic
  - post minor surgery
  - post surgical
- Severity (see [Table 9-3](#) for definitions)
  - mild/moderate, severe
  - classification and recording of severe bleeding episodes is the responsibility of the investigator

---

- Treatment, if any
  - Trial product administration(s)
    - Dose, date, time (see section [7.1.2](#))
  - Other medicinal treatments related to the bleeding episode (haemostatic treatment e.g. tranexamic acid, pain relieving medication etc.)
    - record as concomitant medication (see section [7.8](#))
- Clinical evaluation of the haemostatic effect for bleeding episodes treated with trial product (see [Table 9-4](#) for the project specific 4-point scales)
- **Only** report the bleeding episode as an AE/SAE if fatal, life threatening or evaluated as related to trial product and/or trial procedure (see [Table 9-5](#))

**Table 9-1 Definition of stop of bleed**

---

Stop time is:	When the patient/parent or LAR experiences/observes signs of cessation of the active bleed such as; pain relief, no increase in swelling/limitation of motion and improvement in other objective signs of the bleeding episode
Stop time is not:	When pain and objective signs of the bleeding episode are completely resolved

---

**Table 9-2 Definitions of bleeding episodes**

---

Category	Definition
Spontaneous	Not linked to a specific, known action or event
Traumatic	Caused by a specific, known action or event (e.g. injury or exercise)
Post Minor surgery	Bleed caused by or after minor surgery procedure
Post-surgical	Bleeds after surgery from the surgical site. Bleeding episodes during surgery does not fall under this category

---

Protocol  
 NN7088-4410

~~CONFIDENTIAL~~

Date:	18 June 2019	Novo Nordisk
Version:	2.0	
Status:	Final	
Page:	39 of 86	

**Table 9-3 Definition of bleeding episode severity and treatment recommendation**

Category	Definition	Treatment recommendation
Mild/Moderate	
Examples: uncomplicated musculoskeletal bleeds (joint, muscular bleeds without compartment syndrome), mucosal- or subcutaneous bleeds
 
Mild/moderate bleeds may occur in other anatomical locations
	Mild/moderate bleeding episodes can be treated at home without contact to the investigator
Severe	
Examples: intracranial, retroperitoneal, iliopsoas and internal neck bleeds; muscle bleeds with compartment syndrome; bleeds associated with a significant decrease in the haemoglobin level (>3g/dL)
 
Severe bleeds may occur in other anatomical locations
 
Bleeding episodes that require hospitalisation
 
All life-threatening bleeding episodes
	Severe bleeding episodes must be treated immediately
Instruction for patients	The patient/parent or LAR must be instructed to contact the investigator immediately if in doubt regarding treatment of a bleeding episode and to discuss what other actions may need to be taken	

